4 DATA SOURCES

At each study site data will be entered on the eCRFs stored on IBM Clinical Development (run by Merge Healthcare, an IBM company). Normal ranges for local laboratory measures will be received directly from laboratories and will be integrated with the clinical database. One master list of randomized trial arm assignments will be uploaded to IBM Clinical Development from DCRI Statistics. Subject data which is downloaded from IBM Clinical Development or received from DCRI Data Export Services will include the randomization assignment. Solithromycin plasma concentrations will be received from a central laboratory and will be integrated with the clinical database. Prior to database lock, programmed computer edit checks will be run against the database to identify discrepancies and verify reasonableness of the data. Queries to resolve discrepancies will be generated and resolved by the sites. Periodically, DCRI Statistics will receive or download from DCRI Data Export Services the eCRF database as Clinical Data Interchange Standards Consortium Study Data Tabulation Model (CDISC SDTM version 3.1.3) datasets. CDISC Analysis Data Model (ADaM version 2.1) datasets will be created by DCRI Statistics for production of tables, figures, and listings. All planned reporting will be based off of CDISC datasets, but in the case of emergent safety data some reporting may occur from the raw eCRF data. Table 4 summarizes the variables and time points when measurements are made during the patient assessment period.

Table 4 Schedule of Assessments and Procedures

Activity	Screening/Baseline (Day -3 through Day -1) ^a	Treatment Period		Follow-Up	
		Treatment Days up to Last Day of Treatment ^b	Last Day of Treatment (+48 hours)	Day 16 Post Randomization ^{c, d} (±4 days)	Day 28 Post Randomization ^d (±4 days)
Informed consent form	X				
Demographic data	X				
Eligibility criteria	X				
Randomization	X				
Medical history	X				
Physical examination	X	X ^c	X	X	
Vital signs ^e	X	X ^c	X	X	
Chest x-ray ^f	X				
Study-required safety labs ^g	X ^h	X ⁱ	X ^j	X ⁱ	X ⁱ
Review of standard-of-care data: Safety labs ^{g, k} Microbiology assessments ^l Radiological imaging ^m Non-pharmacological treatments ⁿ	X	X	X	X	
Pregnancy test ^o	X	X ^p			
Concomitant medications ^q	X	X	X		
Study drug or comparator administration ^r		X	X		
Pharmacokinetic sampling ^s		X	X		
Adverse event assessment	X	X	X	X	

Activity	Screening/Baseline (Day -3 through Day -1) ^a	Treatment Period		Follow-Up	
		Treatment Days up to Last Day of Treatment ^b	Last Day of Treatment (+48 hours)	Day 16 Post Randomization ^{c, d} (±4 days)	Day 28 Post Randomization ^d (±4 days)
Serious adverse event assessment	X	X	X	X	X
Clinical outcomes and symptom assessments: Early Clinical Response, End of Treatment, and Follow-Up Post Treatment ^f	X	X ^u	X ^v	X ^w	

- a Screening/baseline can occur up to 72 hours prior to randomization. Standard-of-care laboratory data and radiological imaging from up to 72 hours prior to randomization may be used as screening procedures. Screening/baseline and first day of treatment may be the same day.
- b Treatment period is 5 to 7 days for solithromycin and 5 to 10 days for comparators. These assessments and procedures may be done prior to Day 3 if the subject is discharged from the hospital before Day 3.
- c Record vital signs for each day available. Physical examinations should be recorded from baseline and the Day 3 to 4 visit (early clinical outcome assessment) and at the Last Day of Treatment visit.
- d Every effort should be made to bring the subject back. If the subject is unable or unwilling to return, the AEs/SAEs must be collected via telephone/other media.
- e Vital signs taken at the closest time post-drug administration should be noted. If vital signs following drug administration are not available, record the first value of the day.
- f Screening chest x-ray does not need to be repeated if a standard-of-care chest x-ray was performed within 72 hours of randomization. Subjects that are outpatient and starting on oral therapy do not need a screening x-ray.
- g Local laboratory; includes hemoglobin, hematocrit, white blood cell count with differential, platelet count, blood urea nitrogen, calcium, serum creatinine, potassium, sodium, aspartate aminotransferase, alanine aminotransferase, alkaline phosphatase, total and direct bilirubin, and albumin.
- h A separate study sample is not required if safety labs above are obtained at baseline per standard of care. If multiple laboratory tests are obtained within 72 hours of randomization, record test results closest to randomization.
- i Every effort should be made to obtain safety labs to include aspartate aminotransferase, alanine aminotransferase, alkaline phosphatase, total and direct bilirubin, and white blood cell count with differential. A separate study sample is not required if safety labs above are obtained within the visit window per standard of care.
- j Safety labs must be collected on the last day of dosing or within 48 hours after the last dose. A separate study sample is not required if safety labs above are obtained on the last day of dosing or within 48 hours after the last dose per standard of care.
- k Record the safety labs if performed per standard of care; if multiple laboratory tests are obtained on the same day, record test results closest to administration of study drug.
- l Microbiological assessments will be recorded if performed per routine medical care. These include cultures from sterile body fluids and molecular and serologic tests for *Mycoplasma pneumoniae* and *Chlamydothila pneumoniae*.
- m Radiological imaging of the chest, including chest x-ray or computed tomography (CT) scan, will be recorded if performed per routine medical care.
- n Non-pharmacologic treatments (such as operative procedures) will be recorded if performed per routine medical care.
- o Female subjects of childbearing potential within 24 hours of first dose.

- p If the screening visit for females occurred greater than 24 hours before receiving the study drug.
- q Medications other than antibiotics taken within 72 hours and all antibiotics taken within 7 days prior to first dose of study drug as well as all concomitant medications through the follow-up visit will be recorded.
- r Solithromycin should be administered approximately every 24 hours and at approximately the same time each day (\pm 4 hours) for 5 to 7 days.
- s Only in subjects receiving solithromycin; central laboratory.
- t Symptoms should be recorded at baseline, the Day 3 to 4 visit (early clinical response) visit, the Last Day of Treatment Visit (end-of-treatment response), and at the Day 16 Follow-Up visit). If the subject is discharged on Day 2 (prior to the Day 3 to 4 visit), the early clinical response assessment will be done on the day of discharge.
- u Early clinical response
- v End of Treatment response
- w Day 16 post randomization response (cure)

5 STATISTICAL ISSUES

5.1 General Analysis Conventions

Descriptive Statistics: For continuous and pseudo-continuous variables, the number of observations, mean, standard deviation, median, twenty-fifth percentile, seventy-fifth percentile, minimum and maximum will be provided. For binary yes/no, categorical, and/or ordinal variables a simple count and percent or tally will be provided. Other statistics may be considered if necessary.

Baseline: The latest recorded measurement available prior to first dose of study drug.

Age Group: Analysis presented “by age group” will use the categories “12 -17 years, inclusive”, “6 - <12 years”, “2 - <6 years”, and “2 months - <2 years.”

Consolidated Age Group: Analysis presented “by consolidated age group” will use the categories “2 months - <6 years” and “6 years – 17 years.”

Drug Route: Analysis presented “by drug route” will categorize Solithromycin patients receiving capsule or suspension formulations of Solithromycin as “PO” and IV solution as “IV,” based on the initial (Day 1) administration route of study drug. Comparator patients will not be categorized by drug route due to the possibility of multiple administration routes being utilized concurrently.

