Ampicillin	150-200 mg/kg/day intravenously in equally divided doses every 6 hours	-
Azithromycin	10 mg/kg intravenously/orally on day 1 [500 mg maximum dose] followed by 5 mg/kg orally every 24 hours [250 mg maximum dose]	10 mg/kg orally on day 1 [500 mg maximum dose] followed by 5 mg/kg orally every 24 hours [250 mg maximum dose]
Ceftriaxone	50-75 mg/kg/day intravenously in equally divided doses every 12 hours; total daily dose should not exceed 2 g	50-80 mg/kg intravenously once daily
Erythromycin	40 mg/kg/day orally every 6 hours	30-50 mg/kg/day orally every 6 hours
Erythromycin lactobionate	15 to 20 mg/kg/day intravenously in equally divided doses every 6 hours	50 mg/kg/day intravenously/orally in equally divided doses every 6 hours

Note: if doses of comparator drugs noted in the dosing table above differ those prescribed per standard of care, a site can use the locally prescribed dose.

IV-to-PO switch:

Subjects receiving an IV comparator drug (i.e., ceftriaxone, ampicillin) in any age group may be switched to oral treatment using amoxicillin-clavulanic acid PO (amoxicillin component, 45 mg/kg every 12 hours; subjects weighing ≥40 kg, 875 mg every 12 hours or 500 mg every 8 hours) or amoxicillin alone (45 mg/kg every 12 hours, up to a maximum of 4 g/day).

Subjects must receive 5 to 10 days of treatment with comparator. The exact duration of treatment may be determined at the investigator's discretion.

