6 to <12	IV/PO	Suspension or Capsules	8 mg/kg	10 mg/kg
2 to <6	IV/PO	Suspension	8 mg/kg	10 mg/kg
2 mo to <2	IV/PO	Suspension	8 mg/kg	10 mg/kg

a. The adult dose should be administered unless the subject weighs <40 kg, in which case they receive 10 mg/kg on the first oral dosing day through Day 7. The capsule dose is rounded upwards to the nearest 200 mg.

Drug formulation and administration route will be decided upon by investigator discretion. Subjects starting with IV dosing may be switched to oral dosing at any time at the clinical discretion of the investigator. Under Protocol version 3.0 subjects starting with oral therapy will receive 5 days of solithromycin treatment and those starting with IV therapy (regardless of if and when they switch to oral therapy), will receive a total of 7 days of solithromycin treatment.

The comparator therapy drug, dose and mode of administration will be selected by the treating provider from those listed in the Study Protocol. The treating provider will make a selection of therapy according to subject weight and geographic region of enrollment, and will be consistent with current treatment recommendations for CABP in children as well as standard of care at the site. Subjects must receive 5 to 10 days of treatment with comparator. The exact duration of treatment may be determined at the investigator's discretion.

In the event that a subject is on an IV comparator medication and switches to an oral formulation of a different comparator drug (IV – PO switch), this will not be counted as a premature discontinuation of drug and will not be counted as an efficacy failure unless the site specifically enters that the initial drug was prematurely discontinued. In the event that a subject changes from a PO comparator medication to an IV formulation, or changes specific comparator drug within the first 5 days but remains taking the same formulation (ie changes from one IV drug to another IV drug, or one PO drug to another PO drug), this will be counted as a premature discontinuation of drug and efficacy failure. If a patient prematurely discontinues comparator drug then all dosing of other medications following the initial drug will be recorded as Concomitant Medications (not as further Comparator Arm dosing).

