9 STUDY DRUG ADMINISTRATION

Study drug administration will be summarized in the safety population, by treatment arm, and by treatment arm stratified within consolidated age group. Subjects randomized to solithromycin will also be presented by age group and formulation. Summaries will include a frequency distribution of number of days of drug administration, summary statistics for solithromycin daily dosing amount, and frequency of active comparator antibiotics. Aggregate summaries of treatment discontinuation will be presented. For solithromycin, a subject will be considered to be prematurely discontinued if drug dosing ceases with <5 days on drug for patients starting on PO therapy, and <7 days on drug for patients starting on IV therapy. For active comparator a subject will be considered to be prematurely discontinued if drug dosing ceases with <5 days on drug, or if discontinuation is precipitated by occurrence of an AE. For the purpose of counting days on drug, any date which contains at least a partial dose will be counted. In earlier versions of the protocol (versions 1.0-2.0), 5 to 7 days of solithromycin IV therapy was allowed. For patients enrolled under those protocol versions, premature discontinuation will be determined as <5 days on drug.

For solithromycin subjects, study drug exposure information will be listed, including administered weight-adjusted dose (mg/kg), start and stop date, number of days of dosing, number of days dosing required by protocol which was in effect at the site at the time, loading dose information if applicable, and formulation. For active comparator subjects, details about the active comparator (drug name, dose, dosing frequency), the start date/stop date, and number of days of dosing will be listed.

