10.3 Additional Safety Analyses

Additional safety analyses include summaries of AEs, descriptive statistical summaries of abnormal laboratory values, frequency distributions and shift tables summarizing abnormal laboratory values, graphs of lab values and vital signs, and summaries of concomitant medications as well as prior medications. Pregnancy test results and non-pharmacological treatments will be listed but not summarized. These analyses will be presented in the safety population using intent-to-treat analysis. Summaries will be produced by treatment arm, drug route, and consolidated age groups (2 months - <6 years, 6 years – 17 years inclusive) with the exception of lab graphs and

shift tables. The lab graphs and shift tables will be summarized by treatment arm, with all age groups combined. Safety data will also be listed by treatment arm, age group, formulation (for solithromycin patients only), and subject, with relevant information such as values, normal ranges, and severity presented.

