10.3.1 Adverse Events

AEs (as defined in section 12.1 of Protocol) will be collected from the time of signing the informed consent and assent (if applicable) through 16 days (± 4 days) after randomization. SAEs will be collected through 28 days (± 4 days) after randomization. AEs will be tabulated by using the Medical Dictionary for Regulatory Activities (MedDRA v18.1) system organ class and preferred term. The treatment emergent adverse event (TEAE) is defined as any AE that has an onset on or after the first dose of either study drug, or any pre-existing AE that increases in severity after dosing with either study drug. Adverse events will be tabulated to show the number of subjects with at least one AE, number of subjects with at least one TEAE, and the number of subjects that experienced each individual count of AEs and TEAEs (e.g., number of subjects with 2 AEs, number of subjects with 3-4 AEs, etc.). Additional summaries will be created for infusion site events as well as TEAEs excluding these infusion site events.

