14.4 Safety Data

Table 14.4.1	Proportion of Subjects Experiencing a Treatment Emergent Adverse Event or Discontinuing Study Drug Due to Related Adverse Event – By Treatment Arm and Age Group
Table 14.4.1.1	Proportion of Subjects Experiencing a Treatment Emergent Adverse Event or Discontinuing Study Drug Due to Related Adverse Event – By Treatment Arm, Age Group, and Formulation
Table 14.4.2	Overview of Adverse Events – By Treatment Arm, Consolidated Age Group, and Drug Route
Table 14.4.2.1	All Treatment Emergent Adverse Events by System Organ Class and Preferred Term – By Treatment Arm, Consolidated Age Group, and Drug Route
Table 14.4.2.1.1	Treatment Emergent Adverse Events by System Organ Class and Preferred Term, Excluding Infusion Site Adverse Events – By Treatment Arm, Consolidated Age Group, and Drug Route
Table 14.4.2.1.2	Treatment Emergent Infusion Site Adverse Events by System Organ Class and Preferred Term – By Treatment Arm, Consolidated Age Group, and Drug Route
Table 14.4.2.2	Overview of Serious Adverse Events – By Treatment Arm, Consolidated Age Group, and Drug Route
Table 14.4.2.3	Treatment Emergent Serious Adverse Events by System Organ Class and Preferred Term – By Treatment Arm, Consolidated Age Group, and Drug Route

Table 14.4.3	Shift from Baseline to Worst Post-Baseline Value: Hematology Tests – By Treatment Arm
Table 14.4.3.1	Abnormal Laboratory Results Summary: Hematology Tests – By Treatment Arm
Figure 14.4.3.2	Worst Post-Baseline vs Baseline Laboratory (Scaled by Normal Values): Hematology Tests – By Treatment Arm
Figure 14.4.3.3	Worst Post-Baseline vs Baseline Laboratory (Scaled by Normal Values): Hematology Tests – By Solithromycin Consolidated Age Group and Drug Formulation
Table 14.4.3.2	Shift from Baseline to Worst Post-Baseline Value: Chemistry Tests – By Treatment Arm
Table 14.4.3.2.1	Abnormal Laboratory Results Summary: Chemistry Tests – By Treatment Arm
Figure 14.4.3.2.2	Worst Post-Baseline vs Baseline Laboratory (Scaled by Normal Values): Chemistry Tests – By Treatment Arm
Figure 14.4.3.2.3	Worst Post-Baseline vs Baseline Laboratory (Scaled by Normal Values): Chemistry Tests – By Solithromycin Consolidated Age Group and Drug Formulation
Table 14.4.3.2.4	Summary of Liver Function Tests – By Treatment Arm
Table 14.4.3.2.5	Summary of Liver Function Tests – By Solithromycin Consolidated Age Group and Drug Route
Figure 14.4.4	Summary Plot of Vital Signs – By Treatment Arm

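### Table 14.4.2.1.2 sets an all-infused solithromycin IV group against a comparator denominator that can include children never infused, which dilutes the comparator infusion-site rate

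*SAP*

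**What the plan says.** SAP 5.1 puts each solithromycin child in a PO or an IV category "based on the initial (Day 1) administration route of study drug". For the other arm it states: "Comparator patients will not be categorized by drug route due to the possibility of multiple administration routes being utilized concurrently".

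SAP 10.3 then sets the breakdown for the additional safety analyses: "Summaries will be produced by treatment arm, drug route, and consolidated age groups". SAP 10.3.1 adds: "Additional summaries will be created for infusion site events as well as TEAEs excluding these infusion site events". The list of outputs in SAP section 12 carries this through as Table 14.4.2.1.2, "Treatment Emergent Infusion Site Adverse Events by System Organ Class and Preferred Term", by treatment arm, consolidated age group and drug route.

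Three other provisions bear on the denominator:

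- Protocol 7.3 allows comparator treatment wholly by mouth.
- SAP 6 defines the safety population as everyone dosed, whatever the route.
- SAP 9 says that for comparator subjects "details about the active comparator (drug name, dose, dosing frequency), the start date/stop date, and number of days of dosing will be listed". Route is not among the named fields.

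**The concern.** An infusion-site event from study drug needs an infusion. Every child in the solithromycin IV category had one. The comparator group has no such restriction, so it can hold children who were never at risk of the event from study drug. A reader who looks across the table, from the IV solithromycin figure to the comparator figure, would see an excess for solithromycin even if the rates among infused children were identical. If the displayed rates were equal, that could hide a higher rate among infused comparator children. The comparator interval would also look tighter than the number of infused children justifies.

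Safety and tolerability is the trial's primary objective, and Protocol 5.2.4.1 reports infusion-site events as a recognised feature of IV solithromycin in adults. A table devoted to these events should compare like with like.

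**Working it through.** The plan states no figure on this point, so there is nothing of its own to reproduce.

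**Inputs**

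- Size: SAP 2 says that fewer than one quarter of 400 were enrolled, so at most 99. At 3:1 (SAP 3.3) that is 99 × 3/4 ≈ 74 solithromycin and 99 × 1/4 ≈ 25 comparator.
- f, the fraction of comparator children given any IV comparator dose: not in the documents. Assumed 30% to 70%.
- g, the IV fraction of the solithromycin arm: not in the documents. 50% is used for illustration.
- r, the true infusion-site event rate among infused children, taken as equal in both arms: assumed 10%, with 20% as an alternative. For scale, the adult IV-to-oral study in Protocol 5.2.4.1 gives 10.4% for infusion site pain and 10.0% for phlebitis, without naming the arm.

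**Dilution.** If events occur essentially only in children given IV study drug, the IV solithromycin group shows r and the unsplit comparator shows about r × f. The spurious difference is r × (1 − f), and the spurious ratio is 1/f whatever r is.

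| f | Comparator shown, r = 10% | Spurious excess | Comparator shown, r = 20% | Spurious excess | Ratio 1/f |
|---|---|---|---|---|---|
| 30% | 3% | 7 points | 6% | 14 points | 3.3 |
| 50% | 5% | 5 points | 10% | 10 points | 2.0 |
| 70% | 7% | 3 points | 14% | 6 points | 1.4 |

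With the comparator denominator limited to infused children, both groups show r and the ratio is 1.0 for every f.

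**Precision.** Infused comparators number 25 × 0.3 = 7.5, about 8, to 25 × 0.7 = 17.5, about 18. At r = 10% the chance of seeing no comparator event is 0.9^8 = 43% to 0.9^18 = 15%. For zero events the exact 95% upper limit is 1 − 0.025^(1/n):

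- n = 25: 13.7%
- n = 18: 18.5%
- n = 8: 36.9%

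So 0/25 would suggest an upper limit of 13.7%, where the children actually at risk support only 18.5% to 36.9%. These figures are for the whole comparator arm. The consolidated age split would make the cells smaller still.

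**Whole-arm totals.** Here the solithromycin figure is diluted as well, to r × g, so the ratio of totals is g/f. With g = 50% this is 1.67 at f = 30%, 1.0 at f = 50% and 0.71 at f = 70%. The totals are fair when the IV fractions match.

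**Can a reader rebuild the denominator from the listing?** Often, but not always. Under Protocol Table 9, dose and frequency mostly separate the routes for rest-of-world amoxicillin (every 6 hours IV; 2 or 3 divided doses orally) and amoxicillin-clavulanic acid. Under 40 kg the latter is 25 mg/kg every 8 hours IV, which is 75 mg/kg/day, against 20 to 60 mg/kg/day orally. At 40 kg or more it is 1000 mg against 500 mg. They do not separate the routes for US azithromycin on Day 1, listed as "10 mg/kg intravenously/orally on day 1 [500 mg maximum dose", or for rest-of-world erythromycin lactobionate, which has one entry for both routes. Nor need they do so where a site uses its locally prescribed dose, as the note under Table 9 allows.

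**The case against.** The convention is disclosed and a reason is given. No passage plans a formal contrast of IV solithromycin with the whole comparator arm, and the safety summaries are descriptive. The column layout is inferred from a title. The r × f relation is approximate: Protocol 8.3.1 allows added gram-positive cover, and SAP 3.4 records antibiotics given after premature comparator discontinuation as concomitant medication. A child on an oral comparator could therefore have an infusion-site event from another drug. SAP 9 also tabulates which comparators were used, which gives a rough idea of the infused share. With 25 comparators at most and r = 10%, only 25 × 0.10 × f, or 0.75 to 1.75, comparator events are expected under the assumed f.

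All of this stands, and it limits the size and certainty of the point. It does not remove the mismatch. Following SAP 5.1 and the table title together still leaves the comparator without an at-risk denominator. The SAP's stated reason rules out mutually exclusive IV and PO labels, but it does not rule out a yes/no flag for any IV dose.

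A reader might go further and infer that the primary safety results are distorted. The documents do not support that: SAP 10.2 analyses both primary endpoints by randomised arm, without a comparator route category. A reader might also take the adult IV-to-oral trial, where infusion-site events led 10 solithromycin and 1 moxifloxacin patients to stop drug or withdraw, as evidence that such events would be missed. Discontinuations of study drug for a related AE are already counted by arm in the second primary endpoint and Table 14.4.1. Finally, a reader might infer that IV-to-oral solithromycin switches prompted by an AE escape the analysis. The AE itself counts in the first primary endpoint, the switch can be traced in the listings, and continued full dosing is not a discontinuation as Protocol 14.1.1 defines it.

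**Conclusion.** The point holds as a minor one, confined to one secondary safety table. As written, the plan presents infusion-site TEAEs for an all-infused solithromycin IV group with a comparator rate whose denominator includes any child treated only by mouth.

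The conclusion rests on three things: the layout inferred from the table title and SAP 5.1; infusion-site events being essentially confined to children given IV study drug; and some comparator children never having been infused. The size depends on f, which is assumed. At f of 30% to 70% the comparator rate is understated by a factor of about 3.3 to 1.4. If every comparator child had an IV dose, there would be no dilution.

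**What to change.** 1. In SAP 5.1, add a comparator flag: any-IV (at least one IV dose of comparator study drug) versus PO-only. Children on both routes at once count as any-IV, which answers the SAP's stated difficulty.
2. In Table 14.4.2.1.2, report infusion-site TEAEs in both arms among children ever given IV study drug, with age groups pooled. Add a PO-only column so that no event is lost.
3. State that IV antibiotics recorded as concomitant medication do not make a child any-IV.
4. Add route to Listing 16.2.4.2.
5. Label the comparison descriptive and non-randomised, because the investigator chooses the route and randomisation is stratified only by age group.

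The cost is some SAP wording, one derived flag and one listing field. The fix relies on comparator route having been recorded. The eCRF is not shown, but SAP 3.4 implies that it was: its rule that begins "In the event that a subject changes from a PO comparator medication to an IV formulation" treats that change as premature discontinuation, while an IV-to-oral change is by default not counted as one. Neither rule can be applied without knowing route. The downside is small comparator cells, about 8 to 18 children under the assumed f, with wide intervals. Those intervals show what the data can support.
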